9.2 Sample Size and Randomization

9.2.1. Sample Size

This project consists of three phases: In Phase 1, we will conduct focus groups with up to 24 depressed adolescents and 24 parents. This should be a large enough sample to gain sufficient feedback on ways to make yoga classes an acceptable and feasible intervention. In Phase 2, we will pilot the yoga intervention in a sample of 12 adolescents. In Phase 3, we will conduct a pilot RCT (n=34; with a possibility of 20 additional adolescents in Study B). In Phases 2 and 3, we will assess feasibility, acceptability, and safety of the interventions and research design, and examine key outcomes within relevant confidence intervals. This phase of the study is not designed to be adequately powered to assess efficacy; rather, it is focused on feasibility, acceptability, and safety. (Text also in DSMP.)

9.2.2. Treatment Assignment Procedures

Participants in Phase 3 will undergo randomization. Eligible individuals who consent to participate will be randomly assigned to yoga or group CBT. There are separate randomization tables for Phase 3/Study A participants and Study B participants. Eligibility (i.e., that the participant meets all inclusion criteria) and group (Study A/B) are determined prior to randomization. Our study statistician who has no contact with study participants and will have no access to outcome data until database lock, will create randomization tables using Microsoft Excel and upload to our data collection system (REDCap) prior to the start of recruitment for the pilot RCT. Randomization will be stratified by gender. We will use variable sized block randomization, with randomly ordered block sizes of 4, 6, or 8.

Study staff will not have access to randomization tables. When a person is deemed eligible, study staff will verify the stratification variables in REDCap and then click the "RANDOMIZE" button.

9.3 Definition of Populations

All data analysis will use the intent to treat population and use all available data. There is no per protocol analysis planned.

9.4 Interim Analyses and Stopping Rules

9.4.1. Interim analysis

There is no interim data analysis plan.

Data analysis of Phase 1 qualitative data will occur during and immediately after data collection in Phase 1.

Data analysis of Phase 2 and 3 data will occur at the end of Phase 2, midway through Phase 3, and at the end of Phase 3 (for feasibility and acceptability outcomes). (Text also in DSMP.)

9.4.2 Halting Rules

If there are any SAEs judged related to the study intervention, we will halt the study intervention until an ad hoc safety review is convened with the SMC, MPIs, and other relevant study staff. The safety review will determine whether the study should continue per protocol, proceed with enhanced monitoring, be further investigated, be discontinued, or be modified and then proceed. (Text also in DSMP.)

Subsequent review of serious, unexpected, and related AEs by the SMC, IRB, the sponsor(s), or relevant local regulatory authorities may also result in suspension of further study interventions. The study sponsor(s) retain the authority to suspend additional enrollment and study interventions /administration of study product for the entire study, as applicable. (Text also in DSMP.)

This study will be stopped prior to its completion if: (1) the intervention is associated with adverse effects that call into question the safety of the intervention; (2) difficulty in study recruitment or retention will significantly impact the ability to evaluate the study endpoints; (3) any new information becomes available during the trial that necessitates stopping the trial; or (4) other situations occur that might warrant stopping the trial. (Text also in DSMP.)

9.5 Outcomes

9.5.1 Primary Outcome

There is no single primary outcome, as this is a treatment development study.

We monitor treatment development outcomes (correspondingly described in Table 5) throughout Phases 2 and 3. Target outcomes were chosen on face validity, clinical experience, and, when available, relevant clinical literature. After the pilot open trial (Phase 2), and at 2 time points throughout the Phase 3 pilot RCT (i.e., after enrolling 17 patients and 34 patients), the scientific team will convene to discuss how our actual procedural outcomes compare to the target outcomes. Discrepancies will result in: 1) investigation (using qualitative or other data) of the reason for the failure to meet this outcome; and 2) discussion amongst the research team. Depending on the nature of the discrepancy, we may modify recruitment procedures, assessment procedures, instructions to participants, instructor training procedures, or other aspects of the trial. In addition, Drs. [name] and [name] and the lead yoga instructor will review any adverse events that are possibly, probably, or definitely related to the study intervention to determine whether any changes need to be immediately made to the yoga instructor manual to prevent such events from occurring in the future.

Primary data analyses will be focused on feasibility and acceptability (see Table 5) using intent-to-treat population. Study measures and endpoints will continue to be collected for all enrolled participants, even in the event of premature discontinuation of the study intervention. To mitigate the problem of missing data, our RAs will try to reach participants to encourage them to schedule/complete the assessment via multiple methods that a participant (and their parent) have said are acceptable, including texting, voicemail, or email.

Table 5. Target Outcomes – Phase 2 and 3.

| Description (Assessment method) | Target |
|--|--|
| Feasibility and Acceptability-- Hatha yoga, CBT | |
| Acceptability (qualitative interview) | Most feedback positive; few substantive negative comments. Negative comments used to enhance procedures. Comments regarding video-based vs.in-person classes used to guide decisions about modality for future research. |
| Credibility at baseline (CEQ) | Average > 15 (i.e., midpoint score between low and high credibility) on each of 3 items |
| Expectancy at baseline (CEQ) | Average > 15 (i.e., midpoint score) on each of 3 items |
| Program satisfaction (CSQ-8) | Average > 24 (or a mean score of 3 on each of the 8 items) |
| Home practice (homework questionnaire) | 70% of yoga participants engage in home practice at least 2 times per week for 8/12 weeks. |
| Class attendance | 70% of all participants complete 8/12 classes. |
| Instructor adherence (Adherence measures) | Yoga instructors achieve at least 80% adherence on a random subset of classes taught |
| Safety | |
| Adverse events (SAFTEE; injuries due to yoga) | No serious adverse events or injuries that are possibly, probably, or definitely related to study participation. Any AEs related to study participation might lead to changes in yoga manual or other relevant study procedures, particularly if AE is unexpected. |
| Feasibility and Acceptability—Research Procedures | |
| Recruitment rate | Average of 3 enrolled per month |
| Retention rate | At least 90% complete M1 assessment, 85% complete M2 assessment, 80% complete post-intervention endpoint (Month 3) assessment, 75% complete M6 and M9 follow-up assessments |
| Completeness of self-report instruments and interviews | All self-report instruments will have at least 80% of items completed; interviews will have at least 90% of items completed |

Note: we will look at outcomes for the entire group of enrolled participants for Phase 2 and Phase

3. In addition, in Phase 3, we will examine outcomes for 2 sets of subgroups:

- Study A vs. Study B
- Pre-COVID enrollment (including those who participated in some in-person and some video classes, which is the majority of the Pre-COVID enrolled group) vs. Post-COVID enrollment (i.e., those who consented and started video-based classes from the start).

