Summary of revisions made: Specified that class is approximately 45 minutes long; Changed the manual that used to guide group CBT; Specified that we will exclude adolescents with a history of a manic episode (but not exclude adolescents with a possible history of a hypomanic episode); expanded recruitment options; Clarified that we may ask the adolescent screening questions by phone prior to talking with the parent; Stated that all participants must meet listed

requirements for inclusion at the phone screen stage in order to have a Baseline 1 (BL1) visit scheduled; Revised the language for how we will discuss homework in the yoga classes; Changed the assessment schedule to include two MINI modules (mania/ hypomania, and suicidality) at M3, M6, and M9; Specified that PHI may be included in a REDCap database that is designated for PHI.

Version Number 2.1.

Version date: 12/5/2019

Summary of revisions made: we added a brief assessment of teen treatment arm preference at baseline.

Version Number 2.2.

Version date: 12/18/2019

We revised inclusion criteria to include, in Phase 3/ study A, participants with QIDS ≥ 10 and with suicide ideation if it is currently being treated.

Version Number 2.3.

Version date: 2/12/2020

We revised procedures so that, in Phase 3, in order to be invited for a baseline visit, teens must score an 8 (rather than 5) or greater on the PHQ-8 on the telephone screen.

Version Number 2.4.

Version date: 3/13/2020

We made provisions for being able to conduct interventions via audio/ videoconferencing should we be unable to hold in-person classes due to COVID-19.

Version Number 2.5.

Version date: 3/20/2020.

Further clarifications regarding risks and benefits of holding classes via videoconference.

Version Number 2.6.

Version date: 3/26/2020

Clarified options for paying participants, and that we would send them REDCap link to be able to view a written version of the oral consent for videoconference.

Version Number 3.0.

Version date: 5/1/2020

Updated protocol to allow for remote recruitment and video-based baseline visit.

Version Number 3.1.

Version date: 10/29/2020.

Clarified inclusion / exclusion criteria for passive vs. active suicide ideation.

Version Number 3.2.

Version date: 12/10/2020

Changed follow-up duration to 6 months.

TABLE OF CONTENTS

| | Page |
|--|------------------------------|
| Clinical Intervention Study Protocol Template | 1 |
| FULL PROTOCOL TITLE..... | 2 |

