In Phase 3, Study A, we will conduct a pilot RCT of hatha yoga vs. group CBT to assess feasibility, acceptability, and safety of these interventions, examine preliminary outcomes of depression, functional impairment, and anxiety, as well as engagement of hypothesized mechanisms of self-compassion, and metacognitive awareness. Participants will be adolescents with depression. Parents will also be invited to participate in assessments regarding their child.

Study B, which will run concurrent to Phase 3, will be for participants who did not meet the depression inclusion criteria or had recent changes in therapy or medications that make them ineligible for Phase 3. Participants will be randomized to Phase 3 groups of hatha yoga or group CBT. Parents will also be invited to participate in assessments regarding their child.

Interventions and Duration

Yoga classes. The manualized hatha yoga program will begin with a 20-minute initial individual session with a yoga teacher, to introduce the participant to yoga and give them a chance to privately ask any questions or express any concerns. Subsequently, participants will be asked to attend one class (approximately 45 mins long) per week for 12 weeks. Participants in Phase 2 will participate for 3 months. Participants in Phase 3 will participate for 6 or 9 months (12 weeks of intervention, 3 or 6 months of follow up).

Phase 3 only - Group CBT. We will provide group CBT for depression.. Participants will attend group sessions for 12 weeks. Participants in Phase 3 will participate for 6 or 9 months (12 weeks of intervention, 3 or 6 months of follow up).

Sample Size and Population

The proposed project will include up to 24 depressed adolescents and 24 parents who participate in focus groups (Phase 1), 12 adolescents in an open trial (Phase 2; also including 12 parents), 34 human subjects in a randomized controlled trial of yoga vs. group Cognitive Behavioral Therapy (CBT) (Phase 3; also including 34 parents), and up to 20 adolescents in Study B (and up to 20 parents). Participants will be adolescents aged 13-18 years old, regardless of gender.

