3. STUDY DESIGN

In Phase 1, we will conduct focus groups with 24 adolescents with depression, with separate but concurrent focus groups for their parents (n=24). We will use focus group feedback to adapt our existing yoga program for use with adolescents. We will also separately solicit feedback from experts in depression, health, and/or yoga in adolescents. We will also create accompanying training materials and an instructor fidelity assessment scale. Enrollment period for this phase will last approximately 4 months.

In Phase 2, we will conduct an open single-arm pilot trial (n=12 adolescents) of our adapted hatha yoga to examine feasibility, acceptability, and safety, and to gather additional feedback from adolescents, parents, and yoga providers to guide further refinement of the manual. Participants will be adolescents with depression who will be in the study for 3 months; they will attend yoga classes once per week for all 3 months. Yoga instructors will also invite participants to engage in home-based yoga practice. We will also invite parents to participate in assessments regarding their child. Enrollment period for this phase will last approximately 4 months

In Phase 3, we will conduct a pilot RCT of hatha yoga vs. group CBT (study A; n=34 adolescents) to assess feasibility, acceptability, and safety of these interventions, examine preliminary outcomes of depression, functional impairment, and anxiety, as well as engagement of hypothesized mechanisms of self-compassion, and metacognitive awareness. Randomization will be blocked and stratified by gender. Participants will be adolescents with depression who will receive their assigned intervention for 3 months and then also have follow-up assessments for 3 or 6 months. We will also invite parents to participate in assessments regarding their child. A blind evaluator will assess outcomes that do not directly reference which study arm participants are enrolled in. Enrollment period for this phase will last approximately 6 or 9 months. All study procedures will occur at Butler Hospital.

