|---|--------------------------|--|---------------------|--|---------------------|-------------------|----------|----------|----------|-------------------------|---------------------------|------|
| SCARED (A/P) | Self-report, blind DB | | X | | | | | | X | X | X | |
| TMS (A) | Self-report, blind DB | | X | | | | | | X | | | |
| SCS (A) | Self-report, blind DB | | X | | | | | | X | | | |
| Yoga Practice (IPAQ format) (A) | Interview, non-blind RA | | X | | | | | X | X | X | X | |
| TRAQ (A/P) | Interview, blind RA | | X | | | | | | X | X | X | |
| CASA (A/P) | Interview, blind RA | | X | | | | | | X | X | X | |
| Psychotherapy Practice Scale – Pt Depression Care Version (A) | Self-report, blind DB | | X | | | | | | | | | |
| PROMIS Sleep disturbance scale (A) | Self-report, blind DB | | X | | | | | | X | | | |
| Demographics (A/P) | Self-report, blind DB | | X | | | | | | | | | |
| MINI (A/P) | Interview, pre-randomiz. | | X | | | | | | | | | |
| MINI Mania/hypomania and Suicidality Modules (A) | Interview, blind RA | | | | | | | | X | X | X | |
| PHQ-8 (A) | Interview, pre-randomiz. | X | | | | | | | | | | |
| Teen treatment arm preference (A) | Self-report, blind DB | | X | | | | | | | | | |
| Perceived Cohesion Scale (A) | Self-report, blind DB | | | | X | | | | X | | | |
| Payment – Adolescent | | | \$30 | | | | | \$20 | \$20 | \$30 | \$40 | \$50 |

| Assessment | Type of Assessment | Phone Screening: (Up to 30 days before BL1) | Baseline 1, Visit 1 | Baseline 2; must occur with 14 days of BL1 | After initial class | Weekly M1, M2, M3 | M1 visit | M2 visit | M3 visit | M6 visit (Phase 3 only) | M9 visit (Phase 3 only)** |
|------------------|--------------------|--|---------------------|--|---------------------|-------------------|----------|----------|----------|-------------------------|---------------------------|
| Payment – Parent | | | \$30 | | | | \$20 | \$20 | \$30 | \$40 | \$50 |

Abbreviations: time points: M1, M2, M3 = months 1, 2, and 3, respectively; M6*, M9* = follow-up assessments at months 6 and 9, RCT only.

Assessee: A = adolescent; P = parent; A/P = both. RA = research assistant; DB = database.

** M9 visit only included for participants who signed a consent form version dated 12/1/2020 or earlier.

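### Does the recruitment target of 3 per month contradict the Phase 3 sample size and enrolment period?

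*Combined protocol and SAP*

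**What the plan says.** Table 5 (Section 9.5.1) lists target outcomes for Phases 2 and 3 together. Its recruitment line reads "Average of 3 enrolled per month".

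Section 3 gives the sizes and enrolment periods:

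- Phase 2: 12 adolescents, with "Enrollment period for this phase will last approximately 4 months".
- Phase 3: a "pilot RCT of hatha yoga vs. group CBT (study A; n=34 adolescents"), with "Enrollment period for this phase will last approximately 6 or 9 months". Up to 20 further adolescents may join Study B at the same time.

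The same pair of durations appears elsewhere with a different meaning. The Précis (Interventions and Duration) says "Participants in Phase 3 will participate for 6 or 9 months", made up of the 12-week intervention plus 3 or 6 months of follow-up. The revision history for version 3.2 records "Changed follow-up duration to 6 months", and the footnote to Table 2 in Section 6.1 explains who has which duration: "M9 visit only included for participants who signed a consent form version dated 12/1/2020 or earlier".

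The note under Table 5 has outcomes examined for the whole enrolled group and, in addition for Phase 3, by Study A versus Study B and by enrolment before or after COVID.

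**The concern.** A target rate, a sample size and an enrolment period are tied together: any two fix the third. For Phase 2 they agree. For Phase 3 they do not, on either printed period. A trial that enrolled at exactly the target rate would be scored as having met it and would still run past the stated period.

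Feasibility and acceptability are the primary analyses in this pilot, and they are meant to prepare for a fully powered non-inferiority trial. If the recruitment criterion were set too low for the trial's own timetable, the pilot could report success on a pace that had not delivered the sample on time. The review step in Section 9.5.1, which looks into missed targets, would then not be triggered by that shortfall. The recruitment line also does not itself say whether Study B enrolments count toward the 3.

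**Working it through.** **Inputs.** Rate 3 per month (Table 5). Phase 2: n = 12, about 4 months (Section 3). Phase 3 Study A: n = 34, about 6 or 9 months (Section 3). Study B: at most 20 (Section 3). Time to enrol = n / rate. Number enrolled = rate × period.

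**Phase 2, as a control.** 12 / 3 = 4.0 months, which is the stated period. The target therefore behaves as a calendar accrual rate.

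**Phase 3, Study A.** 34 / 3 = 11.3 months.

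| Printed period | Enrolled at 3 per month | Short of 34 | Rate needed | Overrun at 3 per month |
|---|---|---|---|---|
| 9 months | 3 × 9 = 27 | 7 | 34/9 = 3.8 per month | 11.3 − 9 = 2.3 months (26%) |
| 6 months | 3 × 6 = 18 | 16 | 34/6 = 5.7 per month | 11.3 − 6 = 5.3 months (89%) |

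**Other readings.**

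- Rate averaged over Phase 2 and Study A together: (12 + 34) / 3 = 15.3 months against 4 + 9 = 13, again 2.3 months over, or 18%.
- All 20 Study B adolescents counted toward the 3: 54 / 3 = 18 months.
- The 28-day month that Section 6.2.4 uses for visit dates: 34 / 3 months of 28 days is 10.4 calendar months, still above 9.

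No reading brings 34 inside 9 months at 3 per month, so the mismatch on the page is real.

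**Where the phrase comes from.** Two alternative values make sense for participation time: it is 6 or 9 months according to which consent version was signed. They make little sense for an enrolment period, which is one interval for the whole phase and does not depend on a participant's consent form. The Phase 3 paragraph of Section 3 also gives follow-up as 3 or 6 months shortly before the enrolment sentence. A follow-up edit that spilled into the enrolment sentence, or a participation time put in the wrong place, explains the wording better than a deliberate accrual plan. This is an inference, because the sentence does say enrolment.

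**What depends on the enrolment period.**

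- Sample size (Section 9.2.1): set for feasibility, with no duration in the argument.
- Phase 3 team reviews against Table 5 (Section 9.5.1): triggered at 17 and 34 enrolled, that is, by count.
- Recruitment oversight (Section 10.3.2): reports reviewed weekly.
- Stopping grounds (Section 9.4.2): recruitment difficulty that threatens evaluation of the endpoints, with no date attached.
- Analyses (Section 9.6): descriptive statistics and within-subject tests by arm.
- The recruitment outcome itself: number enrolled divided by months actually elapsed, compared with 3. The planned period does not enter.

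**The case for a change.** The strongest case for a change is this. Recruitment rate is one of the primary feasibility targets, Phase 2 shows that 3 per month was meant as a calendar rate, and 'approximately' does not stretch from 9 months to 11.3. If the phrase is a slip, Section 3 is still wrong and Phase 3 has no stated enrolment period. Correcting one sentence and saying which enrolments count would cost almost nothing.

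The mismatch stands, and the sentence is worth tidying if the document is reopened for another reason. The rest is weaker.

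- The neighbouring entries in Table 5 are mostly minimums, and Section 9.5.1 says the targets rest on plausibility, experience and, where available, literature. They were not derived by dividing 34 by a period. A success threshold below the hoped-for pace is not a contradiction.
- A pace at that minimum would not go unseen, given weekly recruitment reports and a recruitment stopping ground.
- The count is mostly settled. Section 4.3 defines Phase 3 enrolment as occurring at the second baseline contact, after randomization. The note under Table 5 puts the whole enrolled group first and adds Study A versus Study B. An analyst would report the overall rate and both subgroup rates. Naming the Study A rate as the one to be judged would redefine a pre-set criterion during the trial.
- Printing 11 to 12 months instead would only restate 34/3. Nothing in the protocol shows that this was the intended period.

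**Conclusion.** No change to the plan follows. On the page, 34 adolescents at 3 per month take 11.3 months against a longest stated period of 9, a gap of 2.3 months or 7 participants. That gap rests on taking 6 or 9 months as a real enrolment period and 3 per month as a forecast. The first is doubtful, because the phrase matches participation time. The second is not what Table 5 claims to be. If the phrase is a slip, the gap disappears and what remains is an unstated period that no procedure uses.

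On either reading, the sample size, the reviews by count, the recruitment monitoring, the analyses and the target of 3 stay as they are. Planning of the later trial would draw on the observed rate, reported overall and by Study A and Study B, and not on the period printed in Section 3. This is a clerical matter whose correction would gain nothing in the conduct or conclusions of the pilot.
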